## 3 OBJECTIVES AND ENDPOINTS

The study has two primary objectives:

1. Identify novel therapies that work in biomarker-defined subgroups of severe asthma patients
2. Optimize the subgroups targeted for treatment by refining the biomarkers and subgroup definitions

To achieve the first objective, we will perform hypothesis tests for comparisons of each intervention to placebo, (independently of the other interventions) for each of the two primary endpoints (defined below). An intervention will be considered efficacious if significant benefit is found with respect to either of the two primary endpoints. To achieve the second objective, we will enroll participants outside the target subgroups and optimize the target subgroup definitions using precision medicine methods performed during the final analysis.

The study also has two secondary objectives:

1. Gain information about potential response/pharmacodynamic biomarkers for selected therapies
2. Explore the safety and effectiveness of selected therapies in adolescent patients with severe asthma

For the first secondary objective, we will identify which response/pharmacodynamic biomarkers could potentially serve as early or intermediate outcomes for an investigation. These biomarkers may prove useful in predicting whether a treatment will be effective with respect to clinical outcomes, which could in turn inform future trials of the treatment. For the second, we will describe trends with respect to the primary efficacy outcomes observed in the adolescent subgroup and determine if the risk profile of an intervention appears to differ between adults and adolescents. We do not expect to have sufficient power for formal hypothesis tests of effects in the adolescent subgroup alone or for a test of age by treatment interactions.

We have defined two primary endpoints:

- 1) FEV1 percent predicted**, assessed prior to bronchodilator administration
- 2) Asthma symptom control**, assessed via the Juniper Asthma Control Questionnaire (ACQ-6)

An intervention will be considered beneficial if it demonstrates improvement with respect to either of the two primary endpoints relative to placebo, and optimization of the subgroup to be targeted by each intervention will be performed taking both primary endpoints into account. See Section 8.1 for details about assessments for each of these two primary endpoints.

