1.3 Other Study Design Changes

We performed a planned blinded interim analysis of the within-subject (between-period) correlation (not adjusted for treatment) for the PrecISE crossover trial design. The analysis was performed on 64 pairs of observations from consecutive crossover periods. The estimated within-subject correlation for the CompEx² endpoint was 0.33, lower than the value of 0.38 assumed for the power analysis and sample size determination specified in the protocol. This is due, in part, to a lower-than-expected CompEx event rate. The estimated within-subject correlation for the other two primary endpoints, FEV₁ and ACQ-6, was 0.7 or higher. Based on this information and external data on within-subject correlation

for FEV₁ and ACQ, 0.7 was used as the within-subject correlation for re-calculating the required sample size.

CompEx is a novel endpoint which combines exacerbations and deterioration events that are not exacerbations. It relies on study participants to record their peak flow, symptoms and rescue use twice daily. Participant compliance with their daily diaries was lower than expected. This information plus the low correlation and its impact on the power available to detect an intervention effect with respect to CompEx contributed to the decision to remove CompEx as a primary endpoint in the study and consider it a key secondary endpoint.

The target sample size of the study has been revised to 395 participants, due to the change from three to two primary endpoints and change in crossover correlation assumptions for the efficacy analysis. The enrollment period has been extended to a duration of 42 months, compared to the originally planned 30 months. The study period has been extended to a duration of 54 months, with the last patient visit expected in December 2024 and safety follow-up expected to conclude in February 2025. The revised study period and sample size should be sufficient to support our investigation of the five interventions currently active in the PrecISE master protocol. We estimate a total of 1000 treatment periods will be available to contribute to the statistical analyses for evaluation of efficacy and optimization of target subgroups for each intervention. With the current study timelines and enrollment goals, each participant should be able to complete a minimum of two treatment periods and a maximum of six, including at least one placebo period, depending on their time of enrollment.

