1.4 Document Disposition

This document describes the planned statistical analyses that will be conducted at interim analysis points and at the completion of the study of each of the interventions. Once the initial unblinded data review has occurred for an intervention, only the blinded statistics team members will be allowed to modify the Statistical Analysis Plan.

2. Objectives, Endpoints, and Estimands

The PrecISE study has two primary objectives:

1. Identify novel therapies that work in biomarker-defined subgroups of severe asthma patients
2. Optimize the subgroups targeted for treatment by refining the biomarkers and subgroup definitions

To achieve the first objective, we will perform hypothesis tests for comparisons of each intervention to placebo, (independently of the other interventions) for each of the two primary endpoints (defined below). An intervention will be considered efficacious if significant benefit is found with respect to either of the two primary endpoints. To achieve the second objective, we will enroll participants inside

and outside the target subgroups and optimize the target subgroup definitions using precision medicine methods.

The study also has two secondary objectives:

1. Gain information about potential monitoring biomarkers for selected therapies
2. Explore the safety and effectiveness of selected therapies in adolescent patients with severe asthma

For the first secondary objective, we will identify which monitoring biomarkers could potentially serve as early or intermediate outcomes for an investigation. These biomarkers may prove useful in predicting whether a drug will be effective with respect to clinical outcomes, which could in turn inform future trials of the drug. For the second, we will describe trends with respect to the primary efficacy outcomes observed in the adolescent subgroup and determine if the risk profile of an intervention appears to differ between adults and adolescents. We do not expect to have sufficient power for formal hypothesis tests of effects in the adolescent subgroup alone or for a test of age by treatment interactions.

For both primary objectives, we have defined two primary endpoints:

- 1) FEV₁ percent predicted, assessed prior to bronchodilator administration (primary)
- 2) Asthma symptom control, assessed via the Juniper Asthma Control Questionnaire (ACQ-6) (primary)

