The best subgroup for an intervention is defined as the subgroup that maximizes the power of detecting a treatment effect under the global null hypothesis relative to its alternative, namely, the null hypothesis that the intervention has no effect on the two primary endpoints, FEV₁ and ACQ-6, and the key secondary endpoint, CompEx, versus the alternative hypothesis that there is an effect on at least one of these endpoints. For a single outcome, this definition is equivalent to maximizing the square root of the size of the subgroup measured by its prevalence in the relevant patient population multiplied by the average treatment effect in the subgroup. This approach to defining the best subgroup reflects not only the treatment effect in the subgroup but also the size of the subgroup. Potential target subgroups with prevalence smaller than 16% will not be considered.

The primary predictive biomarkers are: blood eosinophils for imatinib, interleukin 6 for clazakizumab, genotypes rs7669660 and rs11547772 for cavosonstat, blood eosinophils for Broncho-Vaxom, and fractional exhaled nitric oxide (FeNO) for MCT. For each of the three outcomes, FEV₁ and ACQ-6 and CompEx, a model like the primary analysis model is fit that includes fixed effects for each biomarker, two-way interactions among the biomarkers, the biomarkers' interactions with treatment, and the biomarkers' two-way interactions with treatment. The one (1) standard deviation method¹⁰ and the overlapping group exponential Lasso penalty approach¹¹ with a penalty term that leads to more likely selection of subgroups defined by a smaller number of biomarkers will be used. Three models will be fitted, one for each outcome. From the fitted model for outcome Y_j , $j = 1, 2, 3$, a set of estimated linear predictors, $\hat{\eta}_1, \dots, \hat{\eta}_n$, is obtained for the set of biomarker vectors through plugging in estimated model coefficients. The target subgroup is then estimated based on a weighted average of three test statistics,

one for each outcome. The best subgroup is the subgroup that maximizes the power of the hypothesis test.

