The resulting subgroup definition will be reported out as the best estimate of the types of patients who should be targeted by the intervention, satisfying the second primary study objective. These results can guide the design of further studies of the interventions found to have benefit in PrecISE. We will estimate the best subgroup for each intervention using primary predictive biomarkers. Then the analysis will be repeated with primary and available secondary predictive biomarkers. The secondary predictive biomarkers include: serum tryptase, sputum polymorphonuclear neutrophils (PMNs), sputum tryptase, and Urinary PGD-2-metabolite for imatinib; high sensitivity C-reactive protein (HS-CRP) for clazakizumab; change in maximal BD FEV₁ for cavosonstat; and urine bromotyrosine for assessment of TH2 inflammation, and assessment of T cell profile in circulation for MCT. The target subgroup will be estimated using the same methodology as specified above. The treatment effect in the estimated subgroup for each intervention will be tested using a 2-fold cross-validation with bootstrap methodology. This methodology preserves the Type I error probability of the testing procedure.

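### SAP 7.8 answers the second primary objective with a subgroup chosen on three outcomes, including CompEx at an unstated weight, while Protocol 3 and SAP 2 tie that objective to FEV1 and ACQ-6

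*SAP*

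**What the plan says.** Two places tie the second primary objective (optimising the target subgroup) to two endpoints:

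- SAP 2: "For both primary objectives, we have defined two primary endpoints". The two listed are pre-bronchodilator FEV1 percent predicted and ACQ-6.
- Protocol 3, after naming the same two: "optimization of the subgroup to be targeted by each intervention will be performed taking both primary endpoints into account".

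SAP 7.8 works with three. Its definition of the best subgroup sets a null of no effect on FEV1, ACQ-6 "and the key secondary endpoint, CompEx, versus the alternative hypothesis that there is an effect on at least one of these endpoints". For estimation, "Three models will be fitted, one for each outcome", and "The target subgroup is then estimated based on a weighted average of three test statistics". The resulting definition is reported as "satisfying the second primary study objective".

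SAP 1.3 records the decision to "remove CompEx as a primary endpoint in the study and consider it a key secondary endpoint". The reasons given are lower than expected diary compliance and a low within-subject correlation (0.33) with its effect on power. A low event rate is mentioned as part of the cause of that correlation. For FEV1 and ACQ-6 the correlation was 0.7 or higher.

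**The concern.** One of the two primary objectives has two endpoint sets in the governing documents, and nothing explains why a key secondary endpoint enters its answer. The weights are also open. Equal weights are mentioned in SAP 7.8 only for a repeat of the cut-off analyses that the section calls exploratory, not for the statistic that picks the reported subgroup.

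Two analysts following the documents could therefore report different target populations for the same intervention. A choice of endpoints or weights made after unblinding would be open to the charge that the data drove it. The reported subgroup matters later: SAP 7.8 tests the treatment effect within it and offers it as a guide to the design of further studies.

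**Working it through.** **Text.** The documents treat the endpoint set as follows.

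| Place | Purpose | Endpoints |
|---|---|---|
| SAP 2 | both primary objectives | FEV1, ACQ-6 |
| Protocol 3 | subgroup optimisation | both primary endpoints |
| SAP 5 and 7.4.1 | declaring efficacy | FEV1, ACQ-6 |
| SAP 7.7.1 | futility | FEV1, ACQ-6 |
| SAP 7.8 | best subgroup, reported for objective 2 | FEV1, ACQ-6, CompEx |

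The mismatch needs no calculation. The rest of this section asks how much it could matter.

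**Reproducing the plan's own figures.** SAP 7.4.1 compares the largest of six statistics (five cut-offs plus all participants) with 2.163 and 2.452. Take nested subgroups of prevalence 1/6, 2/6, ..., 1, with correlation √(smaller prevalence / larger prevalence) between their statistics. Two million draws give 2.163 at one-sided 0.05 and 2.452 at 0.025. The null futility probability of 0.74 in SAP 7.7.1 is also recovered: both statistics fall below 1.29 with probability 0.860 when their correlation is √(2/3), and 0.860² = 0.740. The same structure is used below.

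**How informative CompEx is.** A paired difference has variance 2(1 − ρ) in SD units. That is 2(1 − 0.70) = 0.60 for FEV1 and ACQ-6, and 2(1 − 0.33) = 1.34 for CompEx. At the same standardised effect, the expected CompEx statistic is √(0.60/1.34) = 0.67 of a primary one, before any loss from missing diaries.

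**Signal-to-noise of the average.** Assume equal weights and a 0.3 SD effect on both primaries in the same subgroup. Let r be the correlation between outcomes, δ the CompEx effect in SD, and x = 0.67 × δ/0.3.

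- Two outcomes: 2/√(2 + 2r).
- Three outcomes: (2 + x)/√(3 + 6r).

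With r = 0 and δ = 0 these are 1.41 and 1.15, a loss of 18%. Setting the two expressions equal gives the CompEx effect at which the third outcome breaks even:

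- r = 0: x = 1.414 × √3 − 2 = 0.449, so δ = 0.20 SD.
- r = 0.3: x = 1.240 × √4.8 − 2 = 0.717, so δ = 0.32 SD.
- r = 0.5: x = 1.155 × √6 − 2 = 0.828, so δ = 0.37 SD.

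**Simulated cut-off selection.** The settings are 111 participants, cut-offs at sextiles, true prevalence 33% to 67%, 200,000 draws per scenario, and CompEx treated as approximately normal with its effect in the same subgroup as the primaries.

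| Outcome correlation | CompEx effect | Correct, two outcomes | Correct, three outcomes |
|---|---|---|---|
| 0 | none | 71-73% | 61-62% |
| 0 | 0.2 SD | 71-73% | 71-73% |
| 0 | 0.3 SD | 71-73% | 75-77% |
| 0.3 to 0.5 | 0 to 0.3 SD | reference | lower by about 1 to 16 points |

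The table agrees with the break-even values.

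**How often the answer changes.** These runs use independent outcomes, with the primaries' true subgroup at 67% prevalence.

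- CompEx null: the chosen cut-off changes in 27% of trials (n = 111) to 30% (n = 84).
- A 0.3 SD CompEx effect confined to a 33% subgroup (n = 111): it changes in 29%, and correct selection falls from 73% to 60%.

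**The case against.** Four counter-arguments deserve weight.

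- **The inclusion looks deliberate.** A reader might infer that SAP 7.8 was simply left over from the time when CompEx was primary. The text does not support that. It calls CompEx the key secondary endpoint, which reflects the demotion, and SAP 7.9.4 also works with three outcomes. This stands: the defect is an unexplained conflict, not a proven oversight.
- **Protocol 3 does not say that only the primaries count**, and Protocol 9.5.6 refers to the SAP for detail. This softens the conflict with the protocol. It does not remove the conflict with SAP 2, which names two endpoints for both primary objectives.
- **CompEx may help.** It includes symptoms and reliever use, which ACQ-6 also covers, so a null CompEx alongside a real ACQ-6 effect is not an obvious default. It is also the only outcome in the selection that includes exacerbations. With independent outcomes and a CompEx effect above about 0.2 SD in the same subgroup, selection improves. But shared content suggests positive correlation, and at correlations of 0.3 to 0.5 three outcomes did worse at every CompEx effect from 0 to 0.3 SD.
- **The stakes are limited.** No formal hypothesis is attached to objective 2 (Protocol 9.1, SAP 3.1), this is a phase 2 proof-of-concept study, and Protocol 9.5.8 lists identification of the best subgroup among exploratory analyses. This stands and lowers the severity.

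The simulation is also not the SAP's method, which uses penalised models with biomarker interactions. Nor does a sextile cut-off apply to cavosonstat, whose biomarker is a genotype.

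**Conclusion.** The mismatch is real and unexplained, and it should be fixed. SAP 7.8 reports for a primary objective a subgroup chosen on an endpoint set that differs from the one SAP 2 declares, with the weights left open.

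Three stronger readings are not supported:

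- That a failed endpoint sets the target population. SAP 1.3 demotes CompEx but keeps it as key secondary, and it is one of three inputs. It can shift the subgroup but need not set it.
- That selection must get worse. Under the stated assumptions the effect runs from a gain of about 4 points to a loss of about 16. It depends on the weights, the outcome correlations and the CompEx effect, none of which the documents fix.
- That efficacy claims are compromised. The tests on FEV1 and ACQ-6 do not use this step.

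The figures illustrate possible size only and rest on equal weights, approximate normality, 0.3 SD effects on both primaries and 111 evaluable participants. The textual conflict rests on none of them.

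**What to change.** Make the change before any unblinded subgroup analysis, through the blinded statisticians as SAP 1.4 requires once an intervention's data have been reviewed unblinded.

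- **Preferred.** In SAP 7.8, define the main best subgroup on FEV1 and ACQ-6: a global null on two endpoints, two models, and a weighted average of two statistics with the weights written down. Report that subgroup for the second primary objective. Keep the three-outcome version, with its own stated weights, as a labelled sensitivity analysis.
- **If the sponsor intends CompEx to count.** Amend Protocol 3 and SAP 2 to name it for the second objective, give the reason in light of SAP 1.3, and fix the weights in SAP 7.8.

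The preferred route costs SAP wording only and needs no new data. Its downside is that a benefit seen mainly on CompEx would no longer shape the main subgroup result, although the sensitivity analysis would still show it. The alternative also needs a protocol amendment.

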## 9.5 STATISTICAL ANALYSES

### 9.5.1 GENERAL APPROACH

An intervention will be considered effective if it is effective on at least one of the two primary outcomes. The analysis model for the final efficacy analysis will take into account the correlations on outcomes assessed for the same patient across the different treatment periods. The final analysis will include pairs of the treatment and matching placebo from the first two periods of the trial, as well as unmatched observations on the same patient. Mixed model repeated measures methods will be used for the primary analysis.

A single futility analysis may be conducted for each intervention during the trial. The objective of the futility analysis is to stop interventions showing no signal of efficacy on either of the two primary endpoints. The final precision medicine analyses will use machine learning methods to optimize the target subgroup definition for each intervention. These methods rely on outcomes assessed for patients both within and outside the target subgroups and may result in changes to the cut-points for a particular biomarker used to delineate the positive and negative patients, or to changes in the biomarker themselves.

---

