7.4 Analysis of Primary Efficacy Endpoints

7.4.1 Statistical Model

The final analysis to assess the efficacy of an intervention will be performed when accrual and follow-up for that intervention are complete and will include biomarker positive and biomarker negative participants randomized to the intervention unless the biomarker negative subgroup is dropped after the interim futility analysis, i.e., cavosonstat. In this case, the primary analysis will include only biomarker positive participants assigned to that intervention. Data from the treatment period in which a participant was randomized to the intervention plus the matched placebo period associated with that participant are included in the final analysis of the intervention. If there is no matched placebo, all placebo periods obtained on that participant are included.

Treatment effects with respect to each of the two primary endpoints (FEV₁ and ACQ-6) will be estimated using a mixed model for repeated measurements (MMRM) that appropriately takes into account the within-participant correlations between periods. The MMRM will include treatment (test vs placebo), time (visit nested within period), subgroup levels and baseline values (FEV₁ and ACQ-6), measured before the first randomization, as fixed effects. The model will also include two-way interactions (fixed effects) between treatment and time and baseline and time. Subgroup-specific treatment effects will be estimated by including subgroup by treatment interaction. Unstructured variance-covariance matrix will be used to model covariances within each treatment period. If the model does not converge with an unstructured variance-covariance matrix, the Toeplitz variance-covariance matrix will be used. The model will include a subject-level random intercept to model between-period correlation. If the model fails to converge, other variance-covariance structures will be evaluated until model convergence is achieved. If the variance-covariance matrix in MMRM cannot be estimated well, we will include more data on the participants in the analysis population for that intervention.

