7.7 Interim Analysis

7.7.1 Futility Interim Analysis

When data are available from approximately 34 biomarker positive participants and approximately 17 biomarker negative participants, an interim analysis will be performed. An intervention will be stopped for futility if the futility boundary is crossed for both primary endpoints in biomarker positive participants and in the combined group of biomarker positive and negative participants. The probability to declare futility if at least one of the two endpoints has the true effect size of 0.3 (the effect size is defined as the treatment effect divided by the standard deviation of the outcome) in the biomarker positive subgroup is at most 0.16. To test for futility, we compute the test of a treatment effect for FEV₁ percent predicted, and ACQ-6. Larger values of the test statistics correspond to more favorable treatment responses. Futility is declared for an endpoint if test statistics for biomarker positives and for the combined sample of biomarker positives and negatives, are both less than 1.29. The intervention must show futility on both endpoints in both samples (biomarker positives and the combined biomarker positive and negative group) to be dropped from the study. Assuming mutual independence of the outcomes, the probability to stop for futility is 0.74 if there is no effect on any of the two endpoints.

Futility is also tested on the biomarker negative sample alone. Enrollment of biomarker negative participants to the intervention is stopped if futility is established. The cutoff for futility in this analysis is 1.08. If the biomarker negative group is stopped for futility, 77 more biomarker positive participants are enrolled. The above sample size is for interventions with a proportion of biomarker positives among all enrolled to the intervention of 67%, assuming the interim analysis is performed at the 0.45 information fraction and a 10% active treatment discontinuation rate is observed. Adjustments might be made if these parameters are different from the above.

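### SAP 7.8 makes no allowance for cavosonstat's biomarker negatives having been stopped on their own poor interim result, which tilts the subgroup answer towards the genotype

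*SAP*

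**What the plan says.** SAP 7.7.1 tests futility in the negatives alone: "Enrollment of biomarker negative participants to the intervention is stopped if futility is established. The cutoff for futility in this analysis is 1.08". SAP 7.4.1 includes both biomarker groups in the final efficacy analysis "unless the biomarker negative subgroup is dropped after the interim futility analysis, i.e., cavosonstat"; in that event "the primary analysis will include only biomarker positive participants assigned to that intervention". The combination test in 7.4.1 also changes its second-stage statistic to positives only after a drop. So the first primary objective is protected against this adaptation.

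The second primary objective is answered in SAP 7.8. It lists the biomarkers ("The primary predictive biomarkers are: blood eosinophils for imatinib, interleukin 6 for clazakizumab, genotypes rs7669660 and rs11547772 for cavosonstat"), and for each outcome "a model like the primary analysis model is fit that includes fixed effects for each biomarker", together with biomarker-by-treatment terms. For a single outcome, the best subgroup is the one "maximizing the square root of the size of the subgroup measured by its prevalence in the relevant patient population" times its average treatment effect. The result is reported as follows: "The resulting subgroup definition will be reported out as the best estimate of the types of patients who should be targeted by the intervention".

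Section 7.8 does not mention interventions whose negatives were dropped. Two places in the protocol bear on whether those negatives are used. Section 9.5.1 says of the subgroup methods: "These methods rely on outcomes assessed for patients both within and outside the target subgroups". Section 9.5.8 bases the search for the best target subgroup on the whole of the available data.

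**The concern.** For cavosonstat the biomarker is the genotype that defines positive and negative, so a genotype-by-treatment term cannot be estimated from positives alone. The negatives available are those whose accrual was stopped because they had done badly: about 17 at the interim, plus any enrolled after the data cut-off. Given the drop, their unadjusted effect estimate is biased downwards. Meanwhile the positives grow to 34 + 77 = 111 participants. The contrast between the groups is therefore pushed towards the a priori subgroup, even if the drug works equally in both.

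What is at stake is the subgroup that SAP 7.8 passes on to further studies. SAP Table 1 puts the cavosonstat target genotype at 64% prevalence, so wrongly preferring it would set aside about 36% of patients.

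**Working it through.** **Inputs**
- Interim size: 34 positives and 17 negatives (SAP 7.3, 7.7.1).
- Cutoffs: 1.29 to stop the intervention and 1.08 to drop negatives; 77 more positives after a drop (SAP 7.7.1).
- Effect 0.3 SD, correlation 0.70, 10% discontinuation (SAP 5, 7.7.1).
- Prevalence of the target genotype: 64% (SAP Table 1).
- Assumed: paired end-of-period differences, normal statistics, independent endpoints, no negatives beyond the interim 17, and a drop that requires both endpoints.

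**Reproducing the plan's figure.** With no effect, the chance that the positive-group and combined statistics (correlation sqrt(2/3)) are both below 1.29 is 0.860 per endpoint. For two independent endpoints, 0.860² = 0.740, against the SAP's 0.74. Similarly Φ(1.08)² = 0.860² = 0.739. The 1.08 cutoff therefore fits a drop rule requiring both endpoints, although 7.7.1 does not say so for negatives.

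**Negative-group estimate given a drop (true effect 0.30 SD in both groups)**
1. Variance of a paired difference: 2(1 − 0.70) = 0.60 SD².
2. Evaluable negatives: 17 × 0.9 = 15.3. SE = sqrt(0.60/15.3) = 0.198 SD.
3. Expected statistic: 0.30/0.198 = 1.515. The chance of falling below 1.08 is Φ(−0.435) = 0.332.
4. E[T | T < 1.08] = 1.515 − 0.363/0.332 = 0.42, which is 0.42 × 0.198 = 0.08 SD.
5. Simulation that also requires the intervention to continue gives 0.087 SD in negatives and 0.31 in positives when one endpoint responds. With both responding, the negatives average 0.083 SD.

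**How often the drop occurs under equal effects.** With one endpoint responding, negatives are dropped and the intervention continues in 24.4% of trials, and futility stops 6.5%. So 0.244/0.935 = 26% of continuing trials have a drop. With both responding the share is 0.108/0.995 = 11%.

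**Interaction.** Take a one-sided 5% test that positives benefit more, with the same sizes. Without selection it rejects 5%. Nearly all those rejections occur when negatives do poorly, so given a drop the rate is about 0.05/0.332 = 15%. Simulation gives 15-16%.

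**The SAP's subgroup criterion.** Positives-only (effect P) beats everyone (negative effect N) when sqrt(0.64)·P > 0.64·P + 0.36·N, that is 0.16·P > 0.36·N, or N < 0.44·P.

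| Basis (equal effects) | Positives-only chosen, dropped trials | Same sizes, no selection |
|---|---|---|
| One endpoint | about 62% | 20% |
| FEV1 and ACQ-6 averaged, both 0.3 | 71-73% | 11-12% |
| CompEx added, all three 0.3 | 47% | 9-10% |

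**Sensitivity of the expected negative effect**

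| Change | Expected estimate (SD) |
|---|---|
| 10 to 17 unselected negatives after the cut-off | 0.17-0.19 |
| Either endpoint alone triggers the drop | 0.21-0.30 |
| Endpoints correlated 0.5 | 0.06 |
| True negative effect is 0 | −0.05 |

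**The case against.** The strongest reply is that SAP 7.8 is silent rather than wrong. It never states that dropped negatives are used, and it fits a model like the primary one, which for cavosonstat contains positives only. That is fair as far as the wording goes. But on that reading the genotype cannot be assessed at all, although 7.8 promises a subgroup for every intervention, and Protocol 9.5.1 and 9.5.8 point to inclusion. Either reading needs SAP text.

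A second reply concerns the assumptions. SAP 7.3 sets a data cut-off and mentions no pause in randomization. A crossover pair takes 16 + 8 + 16 = 40 weeks, so some unselected negatives after the cut-off are likely. The both-endpoints drop rule is inferred. Under an either-endpoint rule with only one endpoint responding, the bias all but disappears. These points stand, and they are why the size is given as conditional.

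Third, the interaction test used here is a yardstick. The 0.1-level test in 7.8 is for monotonicity. The genotype analysis uses a lasso penalty, which was not modelled, and a weighted average of three statistics, one of which (CompEx) is not in the drop rule. This stands too. The criterion-based rates, including the CompEx row, are closer to the planned analysis. The cross-validation with bootstrap in 7.8 does not answer the point, because it resamples the same selected negatives.

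Fourth, no formal hypothesis attaches to the second objective, and Protocol 9.5.8 calls the search exploratory. That limits the severity. But SAP 7.8 still reports the result as answering a primary objective.

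A reader might also infer that the subgroup effects in SAP 7.4.1 carry this bias for cavosonstat. The documents do not support that, because after a drop that analysis has positives only.

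**Conclusion.** The point holds in conditional form. SAP 7.8 has no provision for negatives stopped on their own result, and the protocol implies that they are used. If they enter unadjusted and the true effect is 0.30 SD in both genotype groups, the estimate in negatives is expected at about 0.08-0.09 SD, and positives-only is favoured on one endpoint in about 62% of dropped trials instead of 20%. This rests on the both-endpoints drop rule, no negatives after the cut-off, correlation 0.70, 10% discontinuation and a simple two-group contrast in place of the lasso.

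Two stronger readings should be resisted. One is that the analysis confirms the genotype by construction. It does not: about 84% of dropped trials show no nominally significant interaction, and the bias is small (−0.05 SD) if negatives truly do not respond. The other is that the cavosonstat efficacy conclusion is compromised. It is not, because the combination test and the restriction to positives allow for the drop. Nor do the documents show that cavosonstat works in negatives; they give no interim results.

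**What to change.** Add to SAP 7.8, for any intervention whose negatives were dropped at the interim:

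1. State that the interim negatives, and any enrolled after the interim cut-off, enter the subgroup analysis.
2. Beside the unadjusted negative-group effect and interaction, report a sensitivity analysis that accounts for the drop rule, such as a confidence interval conditional on the drop, and the estimate from any unselected later negatives. This should not rest on a truncated-likelihood point estimate, which is unstable near the cutoff: an observed 0.18 SD would become 1.24 SD.
3. Do not report the unadjusted 7.8 result as confirming that the genotype is predictive or is the best subgroup. Describe the genotype as the pre-specified subgroup, and state the selection limit.

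The sensitivity analysis also needs SAP 7.7.1 to say whether dropping negatives requires futility on both endpoints.

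The cost is some SAP wording and a little more analysis, with no new data. The price is wider intervals and a weaker statement for cavosonstat on the second objective.
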